The primary aim is: To evaluate the safety and tolerability of fecal transplant through rectal and oral capsular routes in cirrhosis and HE from a liver disease and symptom standpoint using analysis of serious adverse events, especially HE recurrence, in a placebo-controlled trial.

Secondary aims are between the groups:

- 1. Safety and tolerability of FMT compared to placebo
 - a. Frequency, severity and relatedness of solicited and unsolicited AEs through day 30
 - b. Occurrence of new potentially transmitted infections through six-months post FMT
 - c. Occurrence of new onset or significant worsening of chronic medical conditions post-FMT
- 2. To define the changes in microbiota composition and function of the stool microbiota after FMT compared to pre-FMT baseline and donor compared to placebo

- 3. To evaluate changes in systemic inflammatory cytokines and endotoxin, quality of life and cognitive function compared to pre-FMT baseline and compared to placebo
- 4. To determine occurrence of new onset or significant worsening of chronic medical conditions through six months post-FMT and compared to placebo
- 5. To evaluate the changes in the microbiota after the second oral FMT vs. placebo compared to baseline values

Inclusion/Exclusion Criteria:

Inclusion criteria:

- A. Cirrhosis diagnosed by either of the following in a patient with chronic liver disease
 - a. Liver Biopsy
 - b. Radiologic evidence of varices, cirrhosis or portal hypertension
 - c. Laboratory evidence of platelet count <100,000 or AST/ALT ratio>1
 - d. Endoscopic evidence of varices or portal gastropathy
 - e. Fibroscan values suggestive of cirrhosis
- B. On treatment for hepatic encephalopathy (patient can be on lactulose and rifaximin)
- C. Age: at least 21 years of age
- D. Able to give written, informed consent (demonstrated by mini-mental status exam>25 at the time of consenting)
- E. Women of child bearing potential must agree to use effective contraception for the duration of the study and for 10 days prior and 30 days after the study
- F. Negative pregnancy test in women of childbearing age

Exclusion criteria:

- A. MELD score >22
- B. WBC count <1000 cells/mm3
- C. Platelet count < 25,000/mm3
- D. TIPS in place for less than a month
- E. Currently on antibiotics apart from rifaximin
- F. Infection at the time of the FMT (diagnosed by blood culture positivity, urinalysis, paracentesis as needed)

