Sample size: Based on the published study with rectal FMT¹⁰, we found that standard of care patients had an 80% chance of hospitalization at 6 months, while FMT had a 20% hospitalization rate. Given that we had used antibiotics for this study, we will assume that rectal FMT alone will have a 30% chance of hospitalization rate without antibiotics. We will also assume that oral FMT alone will have a similar hospitalization rate, and their combination will have a 10% hospitalization rate. Using a significance level of α =0.05, a sample size of 25 per group will provide a power of 100% between groups, 20 per group will give a power of 98% to define differences between the groups, while a sample size of 15 patients per group will give a power of 94% between the groups. Therefore, we will enroll 100 patients (25 in each group) for this trial. This sample size calculation will also be valid when we include the second oral FMT with a sample of 10 per group giving 88% power, 15 per group giving 97% power and 25 giving 99% power.

Specialized analyses:

Inflammatory milieu: We will perform the analysis for endotoxemia using the validated Limulus amebocyte lysate (LAL) assay and serum inflammatory cytokines (IL-6, TNF, IL-1b) using ELISA at [name] and [name]'s laboratory at the McGuire VAMC or at Assaygate¹⁴.

Microbial Analysis: Bacterial community composition in stool will be characterized using OTU counts generated as described above. OTU counts will be converted to measures of relative abundance to account for variation in sequencing coverage between samples and compared to the donor sequence. Statistical analysis will be carried out using the statistical software package R. Alpha (α) diversity (richness and evenness of taxa within a population) will be reported using the Shannon Index¹⁵ and Chao1 richness estimator¹⁶. Changes in abundance of individual taxa will also be analyzed using traditional univariate statistical methods. We will use LEfSe (Linear discriminant analysis Effect Size) to determine the features most likely to explain differences. All comparisons will be performed between treatment arms, to gauge donor engraftment in the three FMT-assigned arms, as well as within groups to compare to their baseline microbial composition¹⁷. These will be performed at George Mason University and University of Minnesota. Functional analysis using bile acids, SCFA and metabolomics will also be performed.

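### Read as written, the within-group comparison with baseline uses LEfSe, which ignores that a patient's stools before and after FMT are paired; those results are conservative and lose power

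*Combined protocol and SAP*

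**What the plan says.** The Microbial Analysis paragraph under Specialized analyses of the combined protocol and SAP sets out these steps:

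- OTU counts become relative abundances "to account for variation in sequencing coverage between samples and compared to the donor sequence".
- Alpha diversity is reported with the Shannon index "and Chao1 richness estimator". The input to Chao1 is not stated.
- Changes in individual taxa "will also be analyzed using traditional univariate statistical methods". These tests are not named, and nothing says whether they are paired.
- LEfSe is the one feature-level method that is named: "We will use LEfSe (Linear discriminant analysis Effect Size) to determine the features most likely to explain differences".
- The next sentence covers all comparisons. They are made between arms, to gauge donor engraftment, "as well as within groups to compare to their baseline microbial composition". It ends with citation 17, the metagenomic biomarker reference.

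The Statistical analysis paragraph gives ANOVA of change scores as the general rule, but refers the microbiota to the specialized section. Secondary aim 2 concerns microbiota change "after FMT compared to pre-FMT baseline and donor compared to placebo", and secondary aim 5 concerns change from baseline after the second oral dose. No paired or patient-blocked method for the microbiota is named anywhere.

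**The concern.** A comparison of a group with its own baseline uses two or more stools from each patient. Gut composition differs between people, so a patient's samples will usually resemble each other more than they resemble other patients' samples. A paired test removes that between-patient variation. The standard LEfSe class test (Kruskal-Wallis, which for two classes is the rank-sum test) leaves it in and treats the samples as independent.

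The resulting error is in the cautious direction: too few rejections under no change, and real shifts missed. With at most 25 patients per arm there is little power to give away, and change from baseline is part of two secondary aims.

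A smaller matter sits beside it. Relative abundance is the only adjustment for sequencing coverage in the visible text, and it cannot do that job for Chao1, which is built from counts of taxa seen once and twice.

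**Working it through.** The plan states no power, effect size, within-patient correlation or read depth for the microbiota, so there is no figure of its own to reproduce. What follows is illustration.

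**Inputs from the plan.** Pairs per arm: 25, since "we will enroll 100 patients (25 in each group) for this trial". Level: 0.05, stated for the hospitalization calculation only ("Using a significance level of α =0.05") and without sidedness.

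**Assumed inputs.** Two-sided test; the same 0.05 for taxa; shift δ = 0.5 SD; within-patient correlation ρ from 0 to 0.7; abundances normal on the scale analysed.

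**Normal approximation.** The mean change has true standard error √(2(1−ρ)/n). An unpaired test uses √(2/n) instead.

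- Paired power = Φ(δ√n / √(2(1−ρ)) − 1.96). At ρ = 0.5: Φ(2.5/1 − 1.96) = Φ(0.54) = 70.5%.
- Unpaired power = Φ((δ − 1.96√(2/n)) / √(2(1−ρ)/n)). At ρ = 0.5: Φ((0.5 − 0.554)/0.2) = Φ(−0.27) = 39.3%.
- Unpaired type I error = 2(1 − Φ(1.96/√(1−ρ))). At ρ = 0.5: 2(1 − Φ(2.77)) = 0.56%. At ρ = 0.3 and 0.7 it is 1.9% and 0.03%.

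**Simulation of the rank tests** (4,000 runs per setting, n = 25 pairs; Monte Carlo standard error at most √(0.25/4000) = 0.8 points):

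| ρ | Rank-sum (unpaired) power | Signed-rank (paired) power | Paired minus unpaired, points | Rank-sum type I error |
|---|---|---|---|---|
| 0 | 38.4% | 37.1% | −1.3 | 4.4% |
| 0.3 | 37.4% | 49.6% | 12.2 | 1.9% |
| 0.5 | 34.8% | 64.6% | 29.8 | 1.0% |
| 0.7 | 32.2% | 86.0% | 53.8 | 0.1% |

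The signed-rank test held its level (4.9 to 5.1%). With 20 pairs and ρ = 0.5, power is 26.6% unpaired and 54.6% paired.

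**Chao1.** In its bias-corrected form, Chao1 = S_obs + f1(f1 − 1) / (2(f2 + 1)), where f1 and f2 are the numbers of taxa seen exactly once and twice. Proportions have no such counts, so the second term vanishes and observed richness is all that remains. In one simulated sample of 10,000 reads this gave 300, against 319 from the counts.

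In one fixed invented community (400 taxa, log-normal abundances, log-SD 2), mean Chao1 on unrarefied counts was:

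| Reads | 2,000 | 5,000 | 10,000 | 50,000 | 100,000 |
|---|---|---|---|---|---|
| Chao1 | 276 | 323 | 353 | 387 | 394 |

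Shannon moved only from 4.23 to 4.32 over the same range. After rarefying every sample to 2,000 reads, Chao1 stayed at 275 to 278 whatever the starting depth.

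**The case against.** The strongest reply is that LEfSe is not the only method. Individual taxa also get univariate tests, and a signed-rank test is one of those, so the team may already intend paired testing. This stands in part. A reader might infer that all within-group microbiota testing ignores the pairing, and the documents do not support that. They leave the univariate tests open, and the loss shown here applies to those tests only if they turn out to be unpaired. The change-score rule in the Statistical analysis paragraph does not settle the matter, because that paragraph refers the microbiota elsewhere.

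Second, the link between LEfSe and the within-group comparison is a matter of reading. The sentence on comparisons may cover every method listed, and citation 17 may be LEfSe's own reference placed one sentence late. Even so, a sentence that covers every method covers LEfSe.

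Third, the documents do not describe LEfSe's internal test. Its independence assumption is a general property of the standard method.

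Fourth, every magnitude is assumed, and at zero correlation nothing is lost. That stands. The direction holds for any positive correlation; the size is unknown for this trial.

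On Chao1, a reader might infer that the plan claims to correct richness for coverage by using proportions. It does not say so. The conversion sentence concerns composition and the comparison with the donor, and Chao1's input is left unstated. The text also points to an earlier description of how OTU counts are generated, which is not in the supplied documents, so depth handling may be covered there. A false difference in richness would further need depth to differ systematically between arms or visits; otherwise unequal depth mainly adds noise.

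**Conclusion.** The concern holds for the LEfSe results on change from baseline. Followed as written, the plan applies an independent-samples rank test to paired stools. Under the assumed inputs above, the power given up against a paired test runs from nothing at zero correlation to roughly 54 points at correlation 0.7. The error is conservative, so it does not manufacture an apparent effect. Its harm is that a real shift may be reported as absent.

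The reach is limited. The pairing problem does not touch the randomized comparison between arms, and the primary endpoint and the sample size do not depend on it. It is worth correcting because change from baseline is part of secondary aims 2 and 5.

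The Chao1 matter is a missing specification and not a stated error. It would matter only if depths are unequal and samples are not brought to a common depth, and it fades as depth rises.

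**What to change.** In the Microbial Analysis paragraph:

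1. For within-group change from baseline (secondary aims 2 and 5), name a paired method: a Wilcoxon signed-rank test per taxon, or a mixed model with a patient random effect, which can also take several visits together. Say whether the univariate tests already mentioned are this method.
2. Restrict LEfSe to displaying features that differ between arms.
3. State that Chao1 is computed from integer counts at one common read depth, and give the rule for choosing that depth.

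The cost is a few sentences and standard R functions, with no new data. Bringing samples to a common depth discards some reads and may drop a few shallow samples.

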Aerobes	Fresh	2.53E+05	1.76E+05
	1 freeze-thaw	4.30E+05	4.43E+05
Anaerobes	Fresh	5.80E+07	3.96E+07
	1 freeze-thaw	6.20E+07	5.29E+06

CFUs per mL of Capsules G3 Microbial Emulsion Matrix

_CFUs per mL of stool homogenized 1:1 (w/v) with buffer containing 12.5% glycerol and 0.9% saline, after one freeze-thaw cycle

	per mL
Aerobes	4.53E+06
Anaerobes	1.47E+09
Spores	2.00E+06

These concentrations will be used for the upcoming trial to ensure that the material concentrations in our older trials are expanded.

- We anticipate providing 5 capsules at a time for the oral FMT and 60ml of the FMT enema.
- The placebo for the oral FMT will be made using identical capsules as the active drug, except it will contain 10%/weight trehalose (the cryoprotectant used in preparation of freeze-dried microbiota) and the rest carboxymethylcellulose. Since the capsules are not transparent and have no specific smell or taste, there should be no difficulty in maintaining double blinding.
- The placebo for the liquid formulation is non-bacteriostatic, sterile phosphate buffered saline containing 10% USP grade glycerol. Each dose will be packaged in individual cryobags, just as the active drug.

Study Design

Overall objective: To determine the effect of dual oral and rectal administration of FMT from a rational donor on clinical outcomes (hospitalizations, brain function, quality of life) and host-microbiota interactions (microbial composition and bile acid composition with systemic and intestinal inflammation), compared to single route of administration and placebo, along with a second oral capsular FMT vs placebo administration in patients with cirrhosis and HE using a randomized, phase II clinical trial.

Design overview:

Four groups of outpatients with cirrhosis will be randomized using random sequence generator into placebo and FMT groups and followed for 6 months under an FDA IND double-blind clinical trial.

Group 1: Dual oral and rectal FMT, Group 2: Oral FMT and rectal placebo, Group 3: Oral placebo and rectal FMT and Group 4: Oral and rectal placebo

A repeat oral capsular FMT vs placebo based on the group assignments above will be provided to every subject in at day 30.

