Brain function: These will be administered at visit 1, visit 4 (one month after the second FMT), and end-of-study by [name] and the coordinator/research assistant. Two validated testing strategies, Psychometric Hepatic Encephalopathy Score (PHES) and EncephalApp Stroop Test, which have norms for the Virginia population will be used¹⁸. The PI and his team are well-published in this field and have been administering these for several years to cirrhotic patients. Both these tests showed benefit in the FMT enema trial published by our group in HE¹⁰. PHES is a recommended battery that defines brain dysfunction in cirrhosis¹⁹. It consists of 5 paper and pencil tests (number connection tests A and B, digit symbol test, line tracing test and serial dotting tests), which form a composite score of standard deviations below an age/education-matched community healthy population. This gives a score ranging between -15 and +4. In addition to this continuous score, covert hepatic encephalopathy can be diagnosed with a score <-4 for our population¹⁸. This test battery takes 15 minutes to complete. EncephalApp Stroop^{18, 20} is a freely available computerized test which consists of an easier "Off" state and a more difficult "On" state. The OffTime+OnTime is the output, which is the time taken to complete 5 correct runs in the Off and On states. The output here can be continuous (seconds in the

OffTime+OnTime) or covert hepatic encephalopathy percentage based on local norms¹⁸. This takes 5-7 minutes to complete.

Quality of Life: This will also be administered at Visit 1, Visit 4, one month after the second FMT, and End-of-Study visit. The Sickness Impact Profile (SIP)²¹ is a validated profile for QOL in cirrhosis that the PI and his team have had several years of published experience²²⁻²⁴. SIP consists of 136 questions that pertain to any issues that patients have experienced in the last 24 hours. It has a composite score, two dimensions (physical and psycho-social) and twelve individual domains that are calculated based on norms. A higher score indicates a worse quality of life. This gives only a continuous score as the output. A copy is shown in the Appendix. [name] and the coordinator/research assistant will perform these.

Endpoints and Plan of Analysis:

Primary Endpoint: FMT-related SAEs including HE recurrence within 6 months

Secondary Endpoints (details below):

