- 1. Safety-related (at 6 months): Liver-related hospitalizations, other serious adverse events (SAE) and adverse events related to interventions.
- 2. Microbiota composition: Stool 16SrRNA sequencing and engraftment of donor into recipients.
- Inflammatory milieu: Endotoxemia (LAL), Systemic inflammatory cytokines (IL-6, TNF, IL-1b using ELISA)
- 4. Bile acid profile and gut-liver mediators expression: Bile acid profile using LC/MS in stool and serum and serum C4 (7α-Hydroxy-4-cholesten-3-one).
- 5. Urinary metabolomics to evaluate gut-microbial markers
- 6. Brain function: Two validated testing strategies, PHES and EncephalApp Stroop Test, and Quality of Life: Sickness Impact Profile (a validated profile for healthrelated quality of life in cirrhosis)

Adjudication: Data and safety monitoring for this study will be provided by the Clinical Science Research & Development (CSR&D) centralized Data Monitoring Committee (DMC). The DMC is provided by CSR&D to ensure independent oversight of the safety and integrity of the project. The DMC is an independent multidisciplinary group, whose members have collectively – through research, education, training, experience, and expertise – the requisite knowledge pertinent to the subject areas to be reviewed. Membership details are available on the CSRD website. The DMC will provide an ongoing independent evaluation of this study focused on safety and feasibility, including participant accrual and retention, adverse events monitoring, and data analyses. Meetings will be held three times per year at which recommendations will range from approval to continue (unconditionally or with conditions to be addressed) to probation or possibly termination, if there are problems with enrollment or safety concerns

All outcomes will be compared between groups as well as post-intervention to baseline.

Visits at VCU and VAMC:

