None of the Veterans included in this study will have any visits at VCU. Non-Veterans will be recruited according the approved VCU protocol and will sign the VCU consent. These potential participants will also be shown the approved VA Consent form in order to provide them the full scope of the study. These non-Veterans will have a choice to perform all subsequent studies at VAMC or only the 2 treatment visits, which are visits 2 and 4. When they first arrive at the VAMC for their in-person visits, they will be asked to sign the VA IRB approved consent form before proceeding. Neither of the treatment visits will be performed at VCU even if the enrollee is a non-Veteran.

[name], who is the PI at both sites, will ensure that subjects meet criteria for enrollment and reporting to both IRBs as necessary. An MOU will be signed.

Safety and hospitalization analysis:

Using detailed FDA-approved protocols, patients will be adjudged based on adverse events and serious adverse events at every visit and during the 6-month follow-up. Any SAEs or deaths in an FMT-randomized group will require the DMC to define the "relatedness" of the event to the FMT. If the DMC votes that this is related to the FMT, then this will be sent to the FDA, and Molecular and Cellular Therapeutics (GMP) facility at the University of Minnesota to invoke stopping rules as detailed below. The safety endpoints will be all-cause hospitalizations, defined as unplanned, non-elective hospitalizations within the 6-month period. The reason for the hospitalization will be analyzed by the investigating team and divided into liver-related, liver-unrelated, planned or elective. The latter two categories will not count towards the study but the first two will be analyzed by the team and submitted to the DMC. Other SAEs will be analyzed per FDA definitions. AEs that do not meet the standards of SAE will be evaluated at each visit and be compiled to define trends in one group compared to the other.

Reasonably foreseeable significant risks:

Physical risks:

- 1. Infection or bruising during blood draw
- 2. Procedure-related adverse events from enema (e.g. perforation, bleeding etc)
- 3. Pill-associated dysphagia
- 4. FMT material-related adverse events (e.g. transmissible infection, allergic reaction)

Psychological/Social risks:

(b) Very small risk of loss of confidentiality and privacy

Specific issues to be captured will be

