1. Study procedure-related adverse events from enema (e.g. perforation, bleeding, etc.)

- 2. FMT material-related adverse events (e.g. transmissible infection, allergic reaction)
- 3. Capsule ingestion-related adverse events (pill-associated dysphagia)

4. Short-term safety: Both solicited and unsolicited adverse events will be recorded by, clinical assessment at all in-person visits. The subjects will have the ability to telephone the study team at any point during the study.

5. Long-term safety: follow-up monthly till 6 months to evaluate for SAEs (listed below).

Solicited AEs throughout the trial will be

- (a) fever:
- (b) diarrhea
- (c) vomiting
- (d) constipation
- (e) GI bleeding
- (f) abdominal cramping and pain
- (g) Development of HE (confusion/altered mental status):
- (h) Development of infections, specifically spontaneous bacterial peritonitis
- (i) New onset or significant worsening of chronic medical conditions
- (j) New potentially transmitted infections

We do not expect the infections to occur at a higher rate than the natural history of cirrhosis at this stage. This is borne out by our enema study, in which the FMT group had no infections. Also, a nasojejunal study performed by Phillip et al in severe alcoholic hepatitis, whose MELD scores were much higher than our proposed patients, did not reveal a poor safety profile. We will monitor for all infections and specifically for spontaneous bacterial peritonitis (SBP).

All safety assessments in FMT will be compared to placebo groups given the advanced nature of the cirrhosis and the association of several of these symptoms in the natural history of the disease

Stop-points or reportable adverse events

Any hospitalization or event that is life-threatening will be deemed a serious adverse event in the FMT group and reported to the IRB, FDA, DMC and Molecular and Cellular Therapeutics (GMP) facility at the University of Minnesota within 72 hours (per usual protocol).

This will include the development of an infection that is gut-based/not gut-based:

Gut-Related

- Spontaneous Bacterial peritonitis
- Infectious diarrheal illnesses

Others

- UTI
- Respiratory
- Skin/soft-tissue
- Bacteremia

Overall Study Halting Rules

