1. Assessment of Severity will be performed compared to baseline symptoms that the patient has at enrollment and according to the adverse event table The severity of AEs will be assessed according to the following definitions:

•Mild (1 change): the AE is noticeable to the patient and/or the Investigator, but does not interfere with routine activity

•Moderate (2 change): the AE interferes with routine activity, but responds to symptomatic therapy or rest

•Severe (3 change): the AE significantly limits the patient's ability to perform routine activities despite symptomatic therapy

• Life threatening (4 change): Potentially life-threatening

2. Assessment of Causality

The Investigator must assess the relationship of any AE (including SAEs) to FMT, as *related* or *not related*, based on clinical judgment and using all available information, and may include consideration of the following factors:
Possible alternative causes of the AE, including the disease under treatment, pre-existing conditions, concomitant use of other drugs, and presence of

environmental or genetic factors

• The temporal association between FMT exposure and onset of the AE

• Whether the manifestations of the AE are consistent with known actions or theoretical toxicity of FMT

The causal relationship between FMT and the AE will be assessed using one of the following categories:

Not Related: An AE is not associated with FMT if:

• Temporal relationship is lacking (e.g., the event did not occur within a reasonable time frame following administration of FMT); or

• Other causative factors more likely explain the event (e.g. pre-existing condition, other concomitant treatments);

Related: An AE is attributed to FMT if:

- There is a positive temporal relationship (e.g. the event occurred within a reasonable time frame following FMT); and
- The AE is more likely explained by FMT than by another cause

To aid this assessment, the Investigator/Sponsor will be helped by the VA Central DMC as mentioned above.

All SAEs, possible transmission of infections, and new or worsening medical conditions possibly related to FMT will be referred to this panel, including ones elicited at the monthly visits. This panel will vote based on their analysis of the data regarding the "relatedness" of the AE.

Reporting Safety Observations by the Investigator /Sponsor

1. Reporting of Non-serious AEs

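### The primary aim is a placebo-controlled SAE analysis, but the primary endpoint counts only FMT-related SAEs, with no relatedness rule tied to it and a required DMC vote only for FMT-randomized groups

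*Combined protocol and SAP*

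**What the plan says.** Under Study Design, the primary aim is to evaluate safety and tolerability "using analysis of serious adverse events, especially HE recurrence, in a placebo-controlled trial". It sets no relatedness condition. Endpoints and Plan of Analysis then gives "Primary Endpoint: FMT-related SAEs including HE recurrence within 6 months". Participants are allocated equally to four groups, Group 4 being placebo by both routes, and "followed for 6 months under an FDA IND double-blind clinical trial".

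Relatedness is covered in three places:

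- Safety and hospitalization analysis: "Any SAEs or deaths in an FMT-randomized group will require the DMC to define the" relatedness of the event, which it does by vote.
- Assessment of Causality: "The Investigator must assess the relationship of any AE (including SAEs) to FMT", as related or not related. A related event needs plausible timing, and FMT must be the likelier explanation. An event better explained by something else, such as a pre-existing condition, is not related. The DMC helps with this assessment, and a closing paragraph refers SAEs to it for a vote.
- Overall Study Halting Rules: several safety-review triggers use graded terms (possible, probable, definite), some of them assessed by the investigator and DMC together.

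On comparison, Endpoints and Plan of Analysis says "All outcomes will be compared between groups as well as post-intervention to baseline". The list of issues to be captured says "All safety assessments in FMT will be compared to placebo groups", because many of these symptoms belong to the course of advanced cirrhosis. Unfiltered outcomes are also planned: all-cause unplanned hospitalization, other SAEs and HE episodes.

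**The concern.** Inclusion criterion B requires every participant to be on HE treatment, so serious events from the underlying disease are expected in all four groups. A placebo-controlled comparison deals with that background by randomization. A relatedness filter replaces it with case-by-case judgement, and the underlying disease is nearly always available as the alternative explanation.

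The filter also has no natural meaning in Group 4, where nobody receives FMT. It could work like for like only if events from all groups were judged in the same way by people masked to assignment. The one mandatory DMC vote in the safety analysis section is instead triggered by allocation.

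At stake is whether the primary result answers the primary aim, and whether two analysts working from the same text would count the same participants.

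**Working it through.** **1. The plan's own figure.** Inputs from Sample size: 6-month hospitalization of 80% (control), 30% (rectal), 30% (oral) and 10% (dual); α = 0.05; stated power 100%, 98% and 94% for 25, 20 and 15 per group. The test is not named. Take a four-group chi-square with 3 df:

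- mean rate = (0.80 + 0.30 + 0.30 + 0.10)/4 = 0.375
- noncentrality = n × (0.425² + 2 × 0.075² + 0.275²)/(0.375 × 0.625) = n × 0.2675/0.2344 = 1.141n
- n = 25, 20, 15 gives 28.5, 22.8, 17.1, and power of 99.8%, 98.8%, 94.9%

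This agrees with the stated figures within one point. The power is for hospitalization with no relatedness condition. The documents give no expected rate of FMT-related SAEs, so no power is stated for the primary endpoint.

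**2. Aim against endpoint.** The aim covers SAEs, especially HE recurrence, against placebo. The endpoint covers only those SAEs judged FMT-related. The endpoint is narrower.

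**3. Which assessment defines the endpoint?**

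| Section | Who decides | Scale | Events covered | Tied to primary endpoint? |
|---|---|---|---|---|
| Safety and hospitalization analysis | DMC vote | related or not | SAEs and deaths in FMT-randomized groups | No |
| Assessment of Causality | Investigator, helped by DMC; panel vote | binary | any AE; all SAEs referred on one reading | No |
| Overall Study Halting Rules | Investigator and DMC, in some triggers | graded | safety-review triggers | No |

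In the causality section's referral sentence, the closing words about possible relation to FMT may qualify the whole list or only its last item. No section says what happens if the investigator and the DMC disagree. An SAE rated possibly related could count on the graded scale and fail on the binary one.

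**4. HE recurrence.** The endpoint wording allows two counts: every HE recurrence, or only FMT-related ones. HE is monitored in every group, but nothing chooses between the two. On either reading, all other SAEs are filtered.

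**5. Illustration of the filter.** In the earlier enema trial (10 per group), Sample size gives 20% hospitalization with FMT: 0.20 × 10 = 2 patients. The account of that trial reports no FMT-associated SAE over 5 months: 0 of 10. A relatedness filter would then remove both. The control group there received no FMT, so only the FMT arm shows the effect.

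For this trial, the Sample size rates imply 0.80 × 25 = 20, 0.30 × 25 = 7.5 (twice) and 0.10 × 25 = 2.5 hospitalized participants, 37.5 in all. Of these, 20/37.5 = 53% are expected in Group 4, the group for which the safety analysis section requires no relatedness vote.

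**The case against.** The strongest reply is that much of this is already covered. The DMC is named directly below the endpoint list and votes on relatedness. The only causality section uses a binary scale, and the graded terms serve the halting triggers, which have another purpose. A reader might infer that no assessor or scale is given at all; the documents do not support that. The gap is that none of these is linked to the primary endpoint.

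A reader might also infer that Group 4 must score zero by rule. That does not follow. The investigator rates any AE, the causality section can be read as referring every SAE to the panel, and hospitalizations go to the DMC with no limit by group. A vote on placebo events is not required by the safety analysis section, but it is not barred either.

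Third, the first secondary aim is safety compared with placebo, and unfiltered hospitalization, SAE and HE outcomes are planned. So it would be wrong to say that the trial has no placebo-controlled SAE comparison. A count of attributed events is also a reasonable descriptive safety measure. What stands against this is that the primary aim itself promises the placebo-controlled analysis, and the primary endpoint does not deliver it.

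**Conclusion.** The concern holds in this form: the primary endpoint is narrower than the primary aim, it is not tied to any one relatedness assessment, and it leaves the status of HE recurrence open. If the safety analysis section is followed as written, ascertainment can differ by allocation in a trial described as double-blind, and Group 4 has no like-for-like count. If the causality criteria are applied, events better explained by cirrhosis are removed, although the plan relies on the placebo comparison to deal with exactly those events.

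The numerical effect cannot be derived from the documents. The contrast of 2 of 10 with 0 of 10 is an illustration only. It assumes that the earlier hospitalizations were SAEs and that 5 and 6 months are comparable. The 53% share assumes the Sample size rates and that hospitalizations are SAEs. The unfiltered comparisons are unaffected, but they do not repair the primary endpoint.

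**What to change.** 1. Define the primary endpoint as participants with at least one SAE or HE recurrence through 6 months, regardless of relatedness, compared across the four groups. Naming HE recurrence alongside SAEs keeps recurrences that do not meet the SAE criteria. Show the HE component separately as well, and state the criterion by which it is counted.
2. Amend Safety and hospitalization analysis so that SAEs and deaths from all four groups go to the DMC relatedness vote, masked to assignment and on one named scale. This fits the reading of Assessment of Causality under which all SAEs are referred. If the graded terms are chosen, state which grades count as related. State whose assessment stands if the investigator and DMC differ.
3. Report FMT-related SAEs by group as a descriptive secondary outcome with exact confidence intervals.
4. State in Sample size that the power is for hospitalization, not for the primary endpoint.

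The cost is an amendment to the primary endpoint wording and DMC votes on placebo-group SAEs. AEs and SAEs are already to be recorded in every group, so no new data collection is needed.
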